Clinical Trial Protocol

Protocol Title: A Multi-Center, Double-Masked Evaluation of the Efficacy and Safety of CSF-1 in the Treatment of Presbyopia

Protocol Number: 18-150-0006

Study Phase: 2b

Investigational Product Name: CSF-1 (pilocarpine hydrochloride 0.2% or 0.4% and diclofenac sodium 0.006%) Ophthalmic Solution

IND 131464

Indication: Presbyopia

Investigators: TBD

Sponsor: Orasis Pharmaceuticals, Ltd
[name]
[name]
[name]

Contract Research Organization:

IRB/IEC:

	Date
Original Protocol:	15 November 2018
Amendment 1:	08 February 2019
Amendment 2:	05 June 2019

Confidentiality Statement

This protocol contains confidential, proprietary information of [REDACTED] and/or Orasis Pharmaceuticals, Ltd. Further dissemination, distribution, or copying of this protocol or its contents is strictly prohibited.

MEDICAL MONITOR

Medical Monitor:	[REDACTED]
	[REDACTED]
	[REDACTED]
	[REDACTED]

[REDACTED] PERSONNEL

Department Sr. Vice President:	[REDACTED]
	[REDACTED]
	[REDACTED]
Project Manager:	[REDACTED]
	[REDACTED]
	[REDACTED]

SYNOPSIS

Protocol Title:	A Multi-Center, Double-Masked Evaluation of the Efficacy and Safety of CSF-1 in the Treatment of Presbyopia
Protocol Number:	18-150-0006
Investigational Products:	
 • CSF-1: pilocarpine hydrochloride (0.2% [low dose])/(0.4% [high dose]) and diclofenac sodium (0.006%) • Pilocarpine hydrochloride (0.2% [low dose])/(0.4% [high dose]) • Diclofenac sodium (0.006%)
Study Phase:	2b
Primary Objective:	
 • To evaluate the efficacy of CSF-1 for the treatment of presbyopia
Secondary Objectives:	
 • To evaluate the safety, tolerability, and efficacy of CSF-1 versus the individual components for the treatment of presbyopia • To evaluate the safety, tolerability, and efficacy (onset and duration) of 2 concentrations of CSF-1 ([0.2%/0.006%] and [0.4%/0.006%]) for the treatment of presbyopia
Overall Study Design:	
Structure:	Multi-center, randomized, double-masked, parallel-group, safety, and efficacy study
Duration:	Approximately 2 to 4 weeks (4 study visits)
Controls:	Individual components of the combination therapy (pilocarpine hydrochloride alone and diclofenac sodium alone)
Treatment plan:	
Visit 1: Qualified subjects will receive 1 drop of Refresh Classic[®] (placebo) instilled to each eye.
 
Visit 2: Following the pre-treatment assessments, qualified subjects will be randomized 1:1:1 to 1 of the following treatment arms: CSF-1 (pilocarpine hydrochloride [0.2%]/diclofenac sodium [0.006%]), pilocarpine (0.2%) alone, or diclofenac sodium (0.006%) alone. All subjects will dose twice daily [REDACTED] in both eyes with a single drop for approximately 1 week.
 
Visit 3: Following the visit 3 assessments, subjects will continue BID dosing [REDACTED] in both eyes for approximately 1 week. Subjects initially randomized to the CSF-1 arm will now receive pilocarpine hydrochloride (0.4%)/diclofenac sodium (0.006%); subjects randomized to the pilocarpine hydrochloride (0.2%) alone arm will now receive pilocarpine hydrochloride (0.4%) alone; and subjects randomized to the diclofenac sodium alone arm will continue dosing with diclofenac sodium (0.006%) alone.

[figure not shown]
Measures Taken to Reduce Bias:	Randomization will be used to avoid bias in the assignment of subjects to treatment and to enhance the validity of statistical comparisons across treatment groups. Double-masked treatment will be used to reduce the potential of bias during data collection and the evaluation of clinical endpoints.
Study Population Characteristics:	
Number of Subjects:	Approximately 150 subjects (3 arms; 50 subjects per treatment arm) will be enrolled.
Condition/Disease:	Healthy adult subjects ages 45 to 64 years who have presbyopia
Inclusion Criteria:	Subjects must : 1. [REDACTED] 4. Have best corrected visual acuity (BCVA) at 40 cm ≥ 0.40 and ≤ 0.90 logarithm of the minimum angle of resolution (LogMAR, approximately between 20/50 and 20/160 Snellen) in at least 1 eye at visit 1 prior to placebo dosing and in the same eye at visit 2 (pre-treatment); 5. [REDACTED]

	9. [REDACTED]
Exclusion Criteria:	
Subjects must not:
 
1. [REDACTED]2. Have known contraindications or a sensitivity to the use of any of the IPs or their components;3. [REDACTED] 
[REDACTED]
 
[REDACTED]
 
[REDACTED]
 
[REDACTED]
 
[REDACTED]
 
[REDACTED]
 
[REDACTED]
 
[REDACTED]
 
[REDACTED]
 
[REDACTED]
 
[REDACTED]

	[REDACTED]
--	------------

	
[REDACTED]
 
19. Have a condition or a situation that in the investigator’s opinion may put the subject at increased risk, confound study data, or interfere significantly with the subject’s study participation, including but not limited to unstable cardiovascular, hepatic, renal, respiratory, gastrointestinal, endocrine, immunologic, dermatologic, hematologic, neurologic, or psychiatric disease.

Study Treatments
	
 • CSF-1: Pilocarpine hydrochloride (0.2% [low dose])/(0.4% [high dose]) and diclofenac (0.006%) • Pilocarpine hydrochloride (0.2% [low dose])/(0.4% [high dose]) • Diclofenac sodium (0.006%) 
All patients will dose BID [REDACTED] in both eyes with a single drop of IP.

Evaluation Criteria:
	

Primary Efficacy Endpoint
	
Percentage of subjects with a ≥ 3-line (15 letter) gain in BCVA at 40 cm, 1-hour post-treatment at visit 3 and visit 4

Secondary Efficacy Endpoints
	
 • [REDACTED] • Percentage of subjects with a ≥ 2-line (10 letter) gain in BCVA at 40 cm at each time point at visit 3 and visit 4 • [REDACTED]

Safety Endpoints
	
 • Adverse events (AEs) (reported, elicited, and observed)

General Statistical Methods and Types of Analyses
 
Analysis Sets:
 
 • Intent-to-Treat Analysis Set – The Intent-to-Treat analysis set (ITT) will include all randomized subjects. Subjects in the ITT will be analyzed as randomized. • Per Protocol Set – The per-protocol (PP) set will include subjects in the ITT who do not have significant protocol deviations that affect the primary endpoint. Protocol deviations 	

will be assessed prior to database lock and unmasking. Subjects in the PP set will be analyzed as treated.

- 
- Safety Set – The safety set will include all subjects who have received at least one dose of the IP. Subjects in the safety population will be analyzed as treated.

Unit of Analysis:

The study eye will be used for all monocular analyses. The fellow eye will inherently be included in all binocular analyses. Both eyes will be displayed and analyzed for all ophthalmic safety variables.

The study eye will be defined as the eye that meets all enrollment criteria. If both eyes meet all enrollment criteria, then the eye with the worse Visit 2 (Day 1) BCVA at 40 cm will be the study eye. If both eyes have the same BCVA at 40 cm, the right eye will be the study eye.

General Considerations:

In general, quantitative/continuous data will be summarized using descriptive statistics (n, mean, SD, median, minimum, and maximum). Qualitative/categorical data will be summarized using frequencies and percentages. Statistical testing, unless otherwise indicated, will be performed at a 2-sided 0.05 significance level.

Safety analyses will be conducted in the safety population.

Hypothesis:

H₀₁: The difference, between study eyes treated with CSF-1 (0.4%/0.006%) and study eyes treated with diclofenac sodium (0.006%), in the percentage of study eyes with a ≥ 3 -line (15 letter) gain in BCVA at 40 cm, 1-hour post-treatment = 0.

H₁₁: The difference, between study eyes treated with CSF-1 (0.4%/0.006%) and study eyes treated with diclofenac sodium (0.006%), in the percentage of study eyes with a ≥ 3 -line (15 letter) gain in BCVA at 40 cm, 1-hour post-treatment $\neq 0$.

H₀₂: The difference, between study eyes treated with Pilocarpine (0.4%) and study eyes treated with diclofenac sodium 0.006%, in the percentage of study eyes with a ≥ 3 -line (15 letter) gain in BCVA at 40cm, 1-hour post-treatment = 0.

H₁₂: The difference, between study eyes treated with Pilocarpine (0.4%) and study eyes treated with diclofenac sodium 0.006%, in the percentage of study eyes with a ≥ 3 -line (15 letter) gain in BCVA at 40cm, 1-hour post-treatment $\neq 0$.

The study will be considered a success if either of the null hypotheses, H₀₁ or H₀₂, are rejected in favor of their corresponding alternative hypotheses, H₁₁ or H₁₂. The overall Type I error of the 2-sided alpha = 0.10 will be preserved through the use of Bonferroni correction procedures testing each hypothesis at a 2-sided alpha = 0.05.

If H₀₁ is rejected and CSF-1 (0.4%/0.006%) is considered a success, then CSF-1 (0.2%/0.006%) will be tested against diclofenac sodium (0.006%) at a 2-sided alpha = 0.05. Similarly, if H₀₂ is rejected and Pilocarpine (0.4%) is considered a success, then Pilocarpine (0.2%) will be tested against diclofenac sodium (0.006%) at a 2-sided alpha = 0.05. Within these hierarchical frameworks, these hypotheses can be tested at a 2-sided alpha = 0.05 while still preserving an overall Type I error of alpha = 0.10.

[REDACTED]

H₁₄: The difference, between study eyes treated with Pilocarpine (0.2%) and study eyes

[REDACTED]

[REDACTED]

[REDACTED]

Sample Size:

Fifty subjects per each of the 3 treatment arms (150 total), yields an 85% power to establish superiority of CSF-1 (0.4%/0.006%) and Pilocarpine (0.4%) to diclofenac sodium 0.006% alone in the percentage of study eyes demonstrating a ≥ 3 -line (15-letter) gain in BCVA at 40 cm, 1-hour post-treatment from the baseline measurement using a Pearson chi-squared test at a 2-sided alpha = 0.05 assuming that the diclofenac sodium 0.006% alone response is 5% and the CSF-1 response is 27%, resulting in an overall 2-sided alpha = 0.10 that accounts for the 2 tests of hypotheses utilizing Bonferroni correction procedures.

[REDACTED]

Primary Efficacy Analysis:

[REDACTED]

Descriptive statistics will be presented for each time point by treatment group. Testing of the percentage of subjects with a ≥ 3 -line (15-letter) improvement from baseline will be completed accounting for the correlations between treatments and periods within a subject using a logistic (binomial error and logit link) model estimated by generalized estimating equation (GEE) methods. Aspects of the model include:

- Response measure: indicator of whether the subject had a ≥ 3 -line (15-letter) improvement from baseline in the assessment of BCVA at 40 cm in the study eye
- Covariate: baseline BCVA at 40 cm in the study eye
- Fixed effect explanatory measures: treatment

- Random effect measure: subject, to account for the correlation between treatments within a subject
- Repeated measures correlation: estimated with an unstructured covariance matrix in the GEE model

Standard errors and confidence intervals (CIs, 90% and 95%) will also be presented for each treatment group and the difference between treatment groups.

[Redacted]

Secondary Efficacy Analysis:

[Redacted]

[Redacted]

[Redacted]

[Redacted]

[Redacted]

Safety Analysis:

Verbatim descriptions of AEs will be mapped to Medical Dictionary for Regulatory Activities (MedDRA) terms and be presented in a data listing. Treatment emergent AEs, those that occur after the first dose of IP, will be summarized by treatment group using frequency and percent for each system organ class (SOC) and preferred term (PT) within each SOC. Similar summaries will also be presented for treatment-emergent AEs (TEAEs) related to IP and by severity. When reporting the incidence of AEs, a subject will only be counted once if they ever experience an event within the SOC and ever experience the individual PT within the specific treatment period. AEs will be reported separately by period.

[figure not shown]
[figure not shown]

TABLE OF CONTENTS

Synopsis	3
Table of Contents	13
List of Abbreviations	16
1 Introduction	17
2 Study Objectives.....	18
2.1 Primary Objective	18
2.2 Secondary Objectives.....	18
3 Clinical Hypotheses.....	18
4 Overall Study Design	18
5 Study Population	21
5.1 Inclusion Criteria.....	21
5.2 Exclusion Criteria	21
5.3 Withdrawal Criteria	23
6 Study Parameters	23
6.1 Efficacy Endpoints.....	23
6.1.1 Primary Efficacy Endpoints.....	23
6.1.2 Secondary Efficacy Endpoints.....	24
6.1.3 Criteria for Effectiveness	24
6.2 Safety Endpoints	24
7 Study Materials.....	24
7.1 Study Treatments	24
7.1.1 Investigational Product.....	24
7.1.2 Instructions for Use and Administration.....	25
7.1.3 Subject Instructions.....	25
8 Study Methods And Procedures	26
8.1 Subject Entry Procedures	26
8.1.1 Overview	26
8.1.2 Informed Consent.....	26
8.1.3 Washout Intervals.....	26
8.1.4 Procedures for Final Study Entry.....	26
8.1.5 Pregnancy.....	27
8.1.6 Methods for Assignment to Treatment Groups.....	27
8.2 Concurrent Therapies and Medical History	27
8.3 Examination Procedures.....	28
8.4 Schedule of Visits, Measurements and Dosing.....	31
8.4.1 Scheduled Visit	31
8.4.2 Unscheduled Visits.....	31
8.5 Compliance with Protocol.....	31
8.6 Subject Disposition	31
8.6.1 Completed Subjects.....	31
8.6.2 Withdrawn Subjects	31
8.6.3 Discontinued Subjects.....	31
8.7 Study Termination.....	31

8.8	Study Duration	31
8.9	Monitoring and Quality Assurance	32
9	Adverse Events	32
9.1	Adverse Event	32
9.1.1	Severity	32
9.1.2	Relationship to Investigational Product	33
9.1.3	Expectedness	33
9.2	Serious Adverse Events.....	33
9.3	Procedures for Reporting Adverse Events	34
9.3.1	Reporting a Suspected Unexpected Adverse Reaction	34
9.3.2	Reporting a Serious Adverse Event	34

LASIK	laser-assisted in-situ keratomileusis
logMAR	logarithm of the minimum angle of resolution
MedDRA	Medical Dictionary for Regulatory Activities
mmHG	millimeters of mercury
mPP	modified per protocol
NSAID	non-steroidal anti-inflammatory drug
OTC	over-the-counter
PP	per protocol
PRK	photorefractive keratectomy
PT	preferred term
RGP	rigid gas permeable
SAE	serious adverse event
SAP	statistical analysis plan
SD	standard deviation
SOC	system organ class
TEAE	treatment-emergent adverse event
VA	visual acuity

1 INTRODUCTION

Most individuals will develop symptoms of presbyopia by age 50 (Truscott 2009), and approximately 50% of the population with presbyopia does not have adequate corrective lenses, resulting in some level of disability when performing tasks requiring near visual acuity (VA) (Holden et al 2008). This resulted in a global burden of presbyopia exceeding 1.8 billion people in 2015 (Holden et al 2008), and prevalence is increasing. The primary symptom of this condition is a progressive blurring of vision when performing near tasks such as reading, sewing, working at a computer, and using a tablet or cellular phone. Other symptoms include headaches and visual fatigue, which impair one's quality of life (Truscott 2009).

The underlying cause of presbyopia is an inability to change optical power (accommodation) (Donders 1864). Accommodation is facilitated by the contraction of the ciliary muscle fibers, which change the shape and location of the crystalline lens of the eye. In response to near vision, the crystalline lens becomes thicker and more rounded in response to the actions of the ciliary muscle fibers (Garner and Yap 1997, Croft et al 2001, Glasser 2006). As an individual ages, the lens becomes stiffer and less amenable to changing shape in response to ciliary muscle activity and this culminates in the symptoms of presbyopia.

The neural mechanism of accommodation is the adjustment of the size of the pupil. Pupil size is determined by the dimensions of sphincter and dilator muscle spindles of the iris. The pupil becomes smaller when the eye accommodates. This reduction in the size of the pupil (termed miosis) improves the resolution of the retinal image by preventing diverging light rays hitting the periphery of the cornea and lens from reaching the retina. Miosis further increases the depth of field of the eye. A relatively small pupil offers increased depth of field in a way similar to that achieved by reducing the aperture of a camera.

Current presbyopia treatment strategies include: corrective lenses with single vision or bifocal/multifocal lenses, corneal refractive surgery, corneal inlay procedures, and intra-ocular lens surgery. Monovision correction improves the near vision of one eye (through the use of lenses, contacts, or surgery) while allowing the other eye to be used for distance vision. This approach has had variable results and may cause disturbances in depth-perception (Fernandez et al 2013). Glasses consisting of a pinhole to block out peripheral rays of light have also been used to improve vision in presbyopia (Emsley 1946, Borish 1975). Pinhole glasses severely restrict the wearer's peripheral vision placing the patient at risk while driving or performing other similar tasks. Lastly, surgical correction of vision in presbyopia includes conductive keratoplasty, laser-assisted in-situ keratomileusis (LASIK), laser-assisted epithelial keratomileusis (LASEK), photorefractive keratectomy (PRK), corneal inlays, and accommodative or multifocal intraocular lenses (IOLs). The results of these procedures are variable, at times inconsistent, and contraindicated in some patient groups (Moussa et al 2017). The inconsistencies regarding the success of some of these procedures of presbyopia treatment indicate a need for alternative strategies.

The treatment proposed here repurposes a muscarinic receptor agonist to stimulate effects on iris and ciliary contractility via stimulation of Muscarinic acetylcholine receptor M3. Pilocarpine, a muscarinic agonist, has been successful in treating cases of dilated pupil following ocular surgery (Patel et al 2002) and a broad spectrum of systemic conditions including botulism (Monaco et al 1998), leprosy (Lana-Peixoto et al 2014), sarcoidosis (Bowie and Givre 2003), and Ross syndrome (Weller et al 1992, Chemmanam et al 2007). Low dose pilocarpine

hydrochloride induced miosis also improves Adie's pupil (a neurological disorder affecting the pupil size) in adults, children (Younge and Buski 1976, Flach and Dolan 1985, Soylev et al 1997, Jacobson and Vierkant 1998, Bartlett and Jaanus 2002), dogs (Gerding et al 1986), and cases of pharmacologically-induced anisocoria (Jacobson and Olson 1993).

Muscarinic receptor agonists are known to induce inflammation (Verbout and Jacoby 2012). Thus, combining a non-steroidal anti-inflammatory drug (NSAID) with pilocarpine hydrochloride may reduce the inflammatory response associated with pilocarpine hydrochloride. Diclofenac sodium is a safe and effective NSAID prescribed for the management of pain following corneal refractive surgery (Narvaez et al 2004, Colin and Paquette 2006, Parker et al 2011), inflammation post-cataract extraction (Flach et al 1998, Kocak et al 1998, Flach and Dolan 2000), and allergic conjunctivitis (Laibovitz et al 1995).

CSF-1 Ophthalmic Solution (CSF-1) was well tolerated and resulted in noticeable miosis after topical application in an investigator-initiated feasibility study. Two additional clinical studies (Phase 2a) demonstrated favorable safety and preliminary efficacy and thus support the continued development of CSF-1 as an ophthalmic solution to treat presbyopia. This is a factorial study to determine the importance of each active ingredient and the impact of increasing pilocarpine hydrochloride concentrations (0.2% versus 0.4%) on the efficacy of CSF-1 for the treatment of presbyopia.

2 STUDY OBJECTIVES

2.1 Primary Objective

The primary objective of the study is to evaluate the efficacy of CSF-1 for the treatment of presbyopia.

2.2 Secondary Objectives

The secondary objectives of this study are:

- To evaluate the safety, tolerability, and efficacy of CSF-1 versus the individual components for the treatment of presbyopia

- [REDACTED]

3 CLINICAL HYPOTHESES

The clinical hypothesis of this study is that CSF-1 (the combination of pilocarpine hydrochloride and diclofenac sodium) is superior and/or safer/better tolerated compared with pilocarpine hydrochloride alone and diclofenac sodium alone (0.006%) in improving near vision in subjects with presbyopia.

[figure not shown]
4 OVERALL STUDY DESIGN

This is a 4-visit randomized, double-masked, multi-center, parallel-group study evaluating the safety and efficacy of CSF-1 compared with pilocarpine hydrochloride alone and diclofenac

sodium (0.006%) alone in approximately 150 subjects with presbyopia. Study design is summarized in [Figure 1](#).

Figure 1 Study Design

5 STUDY POPULATION

Approximately, 150 healthy adult subjects between 45 and 64 years of age with presbyopia who do not have any conditions, in the investigator's opinion, that may put the subject at increased risk, confound study data, or interfere significantly with the subject's study participation.

5.1 Inclusion Criteria

Subjects must:

1. [REDACTED]
4. Have BCVA at 40 cm ≥ 0.40 and ≤ 0.90 logarithm of the minimum angle of resolution (LogMAR, approximately between 20/50 and 20/160 Snellen) in at least 1 eye at visit 1 prior to placebo dosing and in the same eye at visit 2 (pre-treatment);
5. Have between -4.50 to +2.00 diopter (D) of sphere in each eye determined by manifest [REDACTED]

5.2 Exclusion Criteria

Subjects must not:

1. [REDACTED]

[REDACTED]

- [REDACTED]
19. Have a condition or a situation that in the investigator's opinion may put the subject at increased risk, confound study data, or interfere significantly with the subject's study participation, including but not limited to unstable cardiovascular, hepatic, renal, respiratory, gastrointestinal, endocrine, immunologic, dermatologic, hematologic, neurologic, or psychiatric disease.

5.3 Withdrawal Criteria

Subjects will be withdrawn from the study if any of the following criteria are met:

- Be a female of childbearing potential who is currently pregnant, nursing, or planning a pregnancy; tests positive to a urine pregnancy test at visit 4; or refuses to use an adequate method of contraception for the duration of the study;
- Have an active ocular infection (bacterial, viral, or fungal), active ocular inflammation (e.g. moderate to severe blepharitis, allergic conjunctivitis, peripheral ulcerative keratitis, scleritis, uveitis) at visit 2, visit 3, or visit 4 in either eye.
- Subjects may also be withdrawn from the study for the following reasons:
 - Adverse event (AE)
 - Lost to follow-up
 - Withdrawal of consent by subject
 - investigator discretion
 - Death
 - Subject not adequately following required study procedures
 - Study terminated by the Sponsor
 - Other

Subject withdrawals will be documented on the subject's source document.

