8.6.3 Discontinued Subjects

A discontinued subject is one who does not complete the 4 protocol-defined study visits. A subject may be discontinued at the discretion of the investigator, sponsor, and/or the institutional review board (IRB). Notification of early discontinuation from the study and the reason for discontinuation will be made to the sponsor and/or [REDACTED].

Prior to discontinuing a subject, every effort should be made to obtain as much follow-up data as possible, and to retrieve all study materials. AEs will be followed as described in Section [9](#).

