10 STATISTICAL HYPOTHESES AND METHODS OF ANALYSES

10.1 General Considerations

In general, quantitative/continuous data will be summarized using descriptive statistics (n, mean, standard deviation [SD], median, minimum, and maximum). Qualitative/categorical data will be

summarized using frequencies and percentages. Statistical testing, unless otherwise indicated, will be performed at a 2-sided 0.05 significance level.

For all variables, baseline is defined as the pre-randomization measurement taken at Visit 2 (Day 1). If the measurement is not available from Visit 2 (Day 1), then the measurement from screening Visit 1 (Day -1 to -14) will be used as baseline for all treatments/visits. Change from baseline will be calculated as follow-up measure minus baseline measure.

The primary analyses of the primary and secondary endpoints will be conducted in the PP, include observed data only, and use statistical models, which adjust for the correlation between treatments within an eye and/or subject.

The secondary analyses of the primary and secondary endpoints will be conducted in the ITT, include observed data only, and use similar statistical models as the primary analyses. No subject data will be excluded from the ITT due to protocol violations/deviations. Sensitivity analysis on the primary efficacy variable will be performed on both the PP and ITT imputing missing data as failures;

Safety analyses will be conducted in the safety population.

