7.2 Per Protocol

The per protocol (PP) set will include subjects in the ITT who do not have significant protocol deviations that affect the primary endpoint. Protocol deviations will be assessed prior to database lock and unmasking. Subjects in the PP set will be analyzed as treated.

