8.5 Adjustment for Multiplicity

For the primary statistical hypotheses described in Section 2.5 of this SAP, the study will be considered a success if either of the null hypotheses, H_{01} or H_{02} , are rejected in favor of their corresponding alternative hypotheses, H_{11} or H_{12} . Rejecting H_{01} and/or H_{02} implies that CSF-1 (0.4%/0.006%) and/or Pilocarpine (0.4%) are significantly ($\alpha = 0.05$) better than diclofenac sodium (0.006%), provided that the difference favors CSF-1 and/or Pilocarpine, in achieving a ≥ 3 -line (15 letter) gain from baseline in BCVA at 40 cm (1-hour post-treatment). This primary efficacy variable was specifically selected to align with the primary objective of the study: to evaluate the efficacy of CSF-1 for the treatment of presbyopia.

The overall Type I error of the 2-sided $\alpha = 0.10$ will be preserved through the use of Bonferroni correction procedures testing each hypothesis individually at a 2-sided $\alpha = 0.05$. If H_{01} is rejected and CSF-1 (0.4%/0.006%) is considered a success, then CSF-1 (0.2%/0.006%) will be tested against diclofenac sodium (0.006%) at a 2-sided $\alpha = 0.05$. Similarly, if H_{02} is rejected and Pilocarpine (0.4%) is considered a success, then Pilocarpine (0.2%) will be tested against diclofenac sodium (0.006%) at a 2-sided $\alpha = 0.05$. Within these hierarchical frameworks, these hypotheses can be tested at a 2-sided $\alpha = 0.05$ while still preserving an overall Type I error of $\alpha = 0.10$. For this Phase 2 study, all secondary and safety endpoints will be tested without adjustment for multiplicity.

9. Disposition of Subjects

Subject disposition will be presented in terms of the numbers and percentages of subjects who were randomized, completed the study, and discontinued from the study. A discontinued subject is someone who does not complete the four protocol-defined study visits. Subjects who are not discontinued from the study will be considered study completers. Disposition will be summarized by treatment arm for all randomized subjects. The reasons for study discontinuation will also be summarized and include: AE, lost to follow-up, physician decision, protocol violation, study terminated by sponsor, withdrawal by subject, and other. A subject listing will be provided which includes the date and reason for study discontinuation.

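### Withdrawing subjects from the study for non-adherence removes their Visit 4 value, so the observed-data ITT repeat can lose the deviators it is meant to keep

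*Protocol*

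**What the plan says.** Protocol 5.3 introduces its second group of reasons with "Subjects may also be withdrawn from the study for the following reasons", and one of them is "Subject not adequately following required study procedures". The wording is permissive, and the withdrawal is from the study, not only from the investigational product. The same list also contains investigator discretion and Other. Protocol 8.6.3 states "A discontinued subject is one who does not complete the 4 protocol-defined study visits" and leaves discontinuation to the investigator, the sponsor or the IRB. It adds a safeguard: "Prior to discontinuing a subject, every effort should be made to obtain as much follow-up data as possible". SAP section 9 tabulates reasons for discontinuation, including "physician decision, protocol violation, study terminated by sponsor, withdrawal by subject, and other".

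On analysis, Protocol 10.1 promises "No subject data will be excluded from the ITT due to protocol violations/deviations", but the same paragraph makes the ITT analyses observed-data only. The visible part of SAP 8.2 says the same for all analyses. The primary analysis uses the PP set (Protocol 10.9.1, SAP 12.1). SAP 12.2 makes its ITT repeat the key secondary analysis. Protocol 10.1 and 10.12 add a sensitivity analysis counting missing values as failures, in both PP and ITT. SAP section 9 has each deviation classified as major or minor in a masked review before the database closes.

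**The concern.** The two high-dose hypotheses, H01 and H02, concern the 0.4% products, which subjects receive only after the Visit 3 assessments. For the two pilocarpine-containing arms, Visit 4 is therefore the only source of a high-dose endpoint value, and the high-dose tests gate the low-dose tests. Visit 3 is also when the first kit is collected and a new diary issued (SAP section 4), so it is a natural moment for non-adherence to come to light. A subject withdrawn then has no Visit 4 value.

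That value could usually still have been measured. The endpoint is read one hour after a dose given by site personnel at the visit (SAP 3.1 and section 4), so missed home doses or diary gaps do not in themselves prevent it.

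At stake is how informative the ITT repeat is. It should show whether the PP result survives when deviators are kept. The more deviators sites withdraw, the closer the observed ITT set comes to the PP set, and agreement between the two says less. If the subjects lost differ in response from those retained, the observed rates shift as well.

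**Working it through.** **Step 1: follow one subject through the rules.** Take a subject randomized to CSF-1 who attends Visit 3, is found not to have followed procedures, and is withdrawn there.

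- ITT membership: retained, because the set is all randomized subjects (Protocol 10.3, SAP 7.1).
- Visit 3 value: retained if already measured.
- Visit 4 value: never collected. The subject is discontinued, and no visible text schedules an assessment after withdrawal.
- Observed-data ITT analysis of the high dose: no value from this subject.
- Missing-as-failure sensitivity analysis: counted as a failure.

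Protocol 10.1 is not breached at any step, because nothing collected is discarded. The promise does not reach data that are never collected.

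**Step 2: reproduce the plan's power.** Inputs from Protocol 10.7: n = 50 per arm, 5% against 27%, Pearson chi-squared, two-sided alpha 0.05 per test. The pooled formula is

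power = Φ{ [Δ√n − 1.96·√(2p̄(1−p̄))] / √(p₁(1−p₁) + p₂(1−p₂)) }

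Here Δ = 0.22 and p̄ = 0.16.

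- Δ√n = 0.22 × 7.071 = 1.556
- 1.96 × √0.2688 = 1.016
- denominator = √(0.0475 + 0.1971) = 0.4946

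The result is Φ(0.540/0.4946) = Φ(1.09) = 86.2%, against the stated 85%. The figure reproduces and is not in dispute.

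**Step 3: equal loss in both arms.** The documents give no withdrawal rate, so the rates below are assumptions. Observed-only power uses the reduced n. Missing-as-failure keeps n = 50 and multiplies both response rates by (1 − loss).

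| Assumed loss | Observed per arm | Power, observed only | Power, missing as failure |
|---|---|---|---|
| 0% | 50 | 86.2% | 86.2% |
| 4% | 48 | 84.8% | 84.5% |
| 10% | 45 | 82.4% | 81.5% |
| 20% | 40 | 77.6% | 75.8% |

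**Step 4: selective loss.** At the planned 27%, an arm of 50 has 0.27 × 50 = 13.5 expected responders. Suppose 5 subjects are withdrawn from CSF-1 only.

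- All 5 non-responders: 13.5/45 = 30.0%. The difference from 5% grows from 22 to 25 points.
- All 5 would have responded: (13.5 − 5)/45 = 8.5/45 = 18.9%.
- 2 withdrawn, both non-responders: 13.5/48 = 28.1%.

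Missing-as-failure gives 13.5/50 = 27.0% in the first case, which is correct there. If the five would have responded at the same 27% as the rest, it gives 0.27 × 45/50 = 24.3%, which is too low. It is right only when those withdrawn were in fact failures.

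**The case against.** Several points on the other side stand.

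- Withdrawal for this reason is optional, and Protocol 8.6.3 asks for follow-up data before a subject is discontinued. A site that follows that request closely may lose little.
- A reader might infer that the plan breaks its own ITT promise. It does not: the promise bars excluding data, the subject remains in the set, and collected values are kept. This is a tension between sections, not a contradiction.
- A reader might infer that the ITT repeat is the only check that keeps deviators in. Missing-as-failure on the ITT retains every randomized subject. Protocol 10.12 also allows pattern-mixture imputation and tipping-point analyses, and the rest of SAP 8.2 is redacted.
- A reader might infer that a withdrawn subject contributes nothing to H01 or H02. The visible model in the Protocol synopsis is a GEE with treatment and baseline BCVA, and diclofenac is the same treatment in both periods. A diclofenac subject's Visit 3 value can therefore still inform the comparator.
- A reader might infer that masked deviation review is bypassed. SAP section 9 makes no exception for withdrawn subjects, and SAP 4.2 masks investigators and staff. What the review cannot do is restore a measurement that was not taken.
- A reader might infer that losses will differ by arm, or that PP and ITT will coincide. Differential adherence is plausible but nothing in the documents shows it. Coincidence is a limiting case in which every major deviator is withdrawn.

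Most visit procedures and the schedules are redacted, so an early-exit assessment could exist there.

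**Conclusion.** The point holds as a gap between the withdrawal rule and the observed-data ITT analysis. On the visible text, a subject withdrawn for non-adherence before Visit 4 stays in the ITT set without a Visit 4 value, although that value could ordinarily have been measured. The harm falls mainly on the key secondary ITT analysis, since the PP primary already removes significant deviators. The request for follow-up data and the missing-as-failure analysis offset it only in part.

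The size cannot be computed from the documents. Under assumed equal losses of 4% to 10%, the power cost is modest: about 1.4 to 3.8 points from 86.2%. The larger risk is selective loss, where five withdrawals confined to non-responders would raise an observed 27% to 30%. These figures rest on the plan's response rates and on assumed withdrawal counts. They illustrate scale and do not predict it.

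**What to change.** Reconcile Protocol 5.3, 8.6.3 and 10.1 with SAP 8.2. State in 5.3 and 8.6.3 that non-adherence alone, without a safety concern or withdrawal of consent:

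- is recorded as a protocol deviation;
- is not by itself a reason to end the scheduled Visit 3 and Visit 4 assessments under any heading, including investigator discretion or Other;
- is handled through the masked PP classification.

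Deleting the single line from 5.3 would not be enough, because the same subjects could leave under those other headings. Keep protocol violation in the SAP section 9 disposition table: it is a reporting category, and removing it would only hide such losses by arm. Whether a non-adherent subject continues investigational product is a clinical matter for the sponsor and investigator, and this change does not address it. Withdrawals for safety or consent are unaffected.

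The cost is a short protocol amendment, a matching SAP sentence and a site memo. The visits are already scheduled. The price is slight dilution of the ITT estimate by less adherent subjects.
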